**Table 9 Pharmacokinetic Parameters of WVE-120101 after Multiple Dose Administration**

Parameter	Definition
$C_{max}$	Maximum observed concentration
$t_{max}$	Time of occurrence of $C_{max}$
$\lambda_z$	Terminal elimination rate constant
$AUC_{0-\tau}$	Area under the plasma concentration-time curve over the dosing interval

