  - m On Day 1, sentinel patients will have blood samples for PK analysis collected predose, 30 minutes ( $\pm 5$  minutes), 1, 2, 4 hours ( $\pm 15$  minutes), 12 hours ( $\pm 2$  hours), 24 hours and 48 hours ( $\pm 4$  hours) postdose. All other patients will have blood samples for PK analysis collected predose and 30 minutes ( $\pm 5$  minutes), 1, 2, 4 hours ( $\pm 15$  minutes), 12 hours ( $\pm 2$  hours), and 24 hours ( $\pm 4$  hours) postdose on Day 1. On Day 112, all patients will have blood samples collected for PK analysis predose and 1, 2, and 4 hours ( $\pm 15$  minutes) postdose. On all other dosing days, PK samples will be collected predose only. On non-dosing days noted, PK will be collected once.
  - n Blood sample for assessment of antibodies to WVE-120101 will be obtained predose (within 1 week prior to injection) or on non-dosing days, as indicated.
  - o On dosing days, CSF sample will be collected  $\leq 15$  minutes prior to study drug administration. No more than 10 mL of CSF total should be collected. CSF samples must be tested locally for safety for the following parameters: total protein, glucose and cell counts (white blood cell counts with differential) on all noted visits.
  - p Immediately after study drug administration, patients should be active for approximately 30 minutes postdose.
  - q All patients will remain in the clinic and have AEs and concomitant medications recorded through 24 hours postdose. In addition, 2 sentinel patients will remain in the clinic and have AEs and concomitant medications recorded throughout the 48-hour postdose period.
  - r This lumbar puncture is optional for patients who terminate early.

**Table 2 Schedule of Assessments for Patients Participating in Both the single and Multiple Dose Portions of the Study (32 mg Cohort)**

Visit	Pre-Screening a	Screening b	Double-Blind Treatment (Single Dose)		Sentinel Patient Follow-up	Follow-up	Double-Blind Treatment (Multiple Dose)			Follow-up		
	1	2	3	4	5	6	7 c	8	9	10 or ET	11	12
Week		-4 to 0	0	0	0	2	4	8	12	16	24	26
Study Day (Visit Window, if applicable) Event/Assessment		Day -28 to -1	Day -6 to Day 1 (Baseline)	Day 2 (24 ± 4h postdose)	Day 3 (48 ± 4h postdose)	Day 14 (±2)	Day 28 (±3)	Day 56 (±3)	Day 84 (±3)	Day 112 or ET (±5)	Day 168 (±5)	Day 182(EOS) (±5) d
Pre-dose/Non-dosing Days												
Patient informed consent form (ICF) Signed	X	X										
Inclusion/exclusion criteria		X	X				X					

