## **10.4 PHARMACOKINETIC ANALYSES**

The plasma and CSF WVE-120101 concentration data will be summarized for patients in the PK population.

The individual patient plasma concentration-time data will be listed and displayed graphically on linear and log scales. The plasma concentration-time data will be summarized descriptively in tabular and graphical formats (linear and log scales).

For each cohort, the plasma WVE-120101 concentration data will be analyzed by noncompartmental PK analysis. The parameters listed in [Table 8](#) and [Table 9](#) will be determined. Additional PK parameters may be evaluated if deemed appropriate. Pharmacokinetic parameters for each dose cohort will be compared across WVE-120101 dose levels.

The CSF concentration data will be summarized in tabular format.

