**Table 8 Pharmacokinetic Parameters of WVE-120101 after Single-Dose Administration**

Parameter	Definition
$C_{max}$	Maximum observed concentration
$t_{max}$	Time of occurrence of $C_{max}$
$AUC_{0-t}$	Area under the plasma concentration-time curve from time zero to the last quantifiable concentration

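### Table 9 promises a terminal rate constant and AUC0-tau after multiple dosing, but 668 of the 672 h after the last dose have no plasma sample

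*Combined protocol and SAP*

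**What the plan says.** Section 10.4 states that, for each cohort, "the plasma WVE-120101 concentration data will be analyzed by noncompartmental PK analysis", that the parameters in Tables 8 and 9 will be determined, and that they will be compared across dose levels. It adds that "Additional PK parameters may be evaluated if deemed appropriate".

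- Table 8 (single dose) lists Cmax, tmax and AUC0-t ("Area under the plasma concentration-time curve from time zero to the last quantifiable concentration"). It lists no rate constant.
- Table 9 (multiple dose) lists Cmax, tmax, lambda-z ("Terminal elimination rate constant") and AUC0-tau ("Area under the plasma concentration-time curve over the dosing interval").

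The samples are set in section 4.2. For the 2-16 mg cohorts, Table 1 footnote m says: "On Day 112, all patients will have blood samples collected for PK analysis predose and 1, 2, and 4 hours" postdose. Table 2 gives the same times on Day 84 for the 32 mg cohort, and Table 3 gives them for treatment-naive patients. For the rest, "On all other dosing days, PK samples will be collected predose only" and "On non-dosing days noted, PK will be collected once". The only PK visit after the last dosing day is Day 140 (Day 112 at 32 mg), with a window of 5 days either side. No plasma PK is marked at Day 196 (Day 168 at 32 mg).

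**The concern.** A terminal rate constant needs several samples in the terminal phase, and an interval AUC needs samples spread over the interval. The last-dose grid has three samples in the first 4 h and one about four weeks later. No other multiple-dose interval is better sampled. Roll-over patients have only predose draws at the two earlier multiple doses, and treatment-naive patients have draws to 4 h after their first dose and then the next predose draw.

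Software will still return a number for both parameters. That number would depend heavily on which points are fitted, how the gap is bridged, and whether the one late sample is quantifiable. It would then be tabulated as exposure and compared across doses. Two of the four Table 9 parameters are affected, under a secondary objective (plasma PK).

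**Working it through.** **From the documents**

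- Dosing interval (section 6.2.2, 4-week intervals): 28 × 24 = 672 h.
- Last early sample: 4 h. Gap: 672 − 4 = 668 h. Share of interval: 668/672 = 99.4%.
- Late draw: last dose ±3 days, follow-up visit ±5 days. If both windows run from nominal study days, the draw falls 28 ± 8 = 20 to 36 days after the dose. If the late window runs from the actual dose, it falls 28 ± 5 = 23 to 33 days after. The documents do not say which.
- Postdose points: 1, 2, 4 and about 672 h. If the highest value is at 1 h, three points follow it. If it is at 4 h, one does.

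The plan states no figure of its own to reproduce here.

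**Illustration, with assumed kinetics**

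The assumed curves have a fast phase with weight 1 − s and a slow phase with weight s:

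- s = 0.02, 0.05 or 0.10
- fast half-life 2, 4, 8 or 12 h
- terminal half-life 120, 240 or 480 h
- entry into plasma instantaneous, or with absorption half-life 0.5, 1.5 or 3 h

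That gives 3 × 4 × 3 × 4 = 144 curves.

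One curve worked through (s = 0.05, fast 4 h, terminal 240 h, instantaneous entry, no earlier doses, predose value 0): C(t) = 0.95·2^(−t/4) + 0.05·2^(−t/240).

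- C(1) = 0.849, C(2) = 0.721, C(4) = 0.524, C(672) = 0.0072.
- True AUC0-672 = 0.95·4/ln 2 + 0.05·(240/ln 2)·(1 − 2^(−2.8)) = 5.48 + 14.83 = 20.3.
- Linear rule, 0-4 h: 0.424 + 0.785 + 1.246 = 2.46. From 4 to 672 h: 668 × (0.524 + 0.0072)/2 = 177.6. Total 180.0, or 8.9 times the truth; the last segment is 177.6/180.0 = 98.6% of it.
- Log rule on declining segments, 4 to 672 h: 668 × (0.524 − 0.0072)/ln(0.524/0.0072) = 80.5. Total 83.0, or 4.1 times the truth. The same samples give 180.0 or 83.0 depending on the rule.
- Log-linear fit on 2, 4 and 672 h: half-life 104 h against a true 240 h, ratio 0.43.

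Across all 144 curves:

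| Quantity | Last dose alone | Earlier doses added |
|---|---|---|
| AUC0-tau, linear rule, estimate/true | 2.7-21.5 | about 2.1-21.4 |
| AUC0-tau, log rule, estimate/true | 2.0-6.4 | about 1.7-6.1 |
| Half-life from 2, 4, 672 h / true | 0.20-0.78 | about 0.2-0.8 |

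In 90 of the 144 curves the fitted 1-4 h slope is upward, so those points offer no declining phase to fit. The true peak falls after 4 h in 45.

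The ranges depend on the assumptions. A second set (absorption rate 1/h, fast half-life 2-8 h, terminal 48-336 h, slow share 1-5%) gave 4.8- to 32-fold (linear) and 2.9- to 7.6-fold (log).

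**Check of the replacement**

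On predose, 1, 2 and 4 h, linear AUC0-4h recovers 0.94-0.98 of the true 0-4 h area with absorption and 0.79-0.86 with instantaneous entry. It covers 2-35% of AUC0-672.

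**The case against.** Section 10.1 leaves analysis detail to the SAP, section 10.3.1 lets the pharmacokineticist judge whether a patient's data are sufficient, and section 10.4 already allows extra parameters such as a partial AUC. An SAP rule could therefore withhold unsupported values. That stands as a route to the fix, but it does not remove the problem. No rule supplies samples between 4 h and 28 days, and the scheduled last-dose grid is the same for every patient, so the population definition cannot pick out better-sampled ones.

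Dose comparisons may suffer less than absolute values. With proportional kinetics and a late sample that is quantifiable at every dose, a common fold-error largely cancels in ratios. That stands too. The cancellation would fail if quantifiability or actual visit timing differed by dose.

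If decline were mono-exponential from 1 h on, the early slope and the log rule would be right. Nothing in the documents shows this.

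Three stronger readings are tempting and not supported:

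- **That the trial's AUC0-tau will be wrong by a known factor.** The documents give neither human plasma kinetics nor a plasma quantification limit, so every fold-error is an assumption.
- **That a rising 1-4 h profile would yield a wrong rate constant.** With no declining phase to fit there, the likelier outcome is a value reported as not estimable.
- **That dose escalation is compromised.** Section 4.3.3 rests escalation on safety data, and the PK analysis is descriptive.

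**Conclusion.** The point holds. The gap of 668 of 672 h comes straight from the schedules and applies to all cohorts and to treatment-naive patients. The noncompartmental analysis that section 10.4 commits to cannot support two of the four Table 9 parameters from these samples. Confidence is high on the gap. The fold-errors are illustrations under the stated biphasic assumptions and should be quoted only as such. The consequence is modest: a descriptive secondary PK report could carry unsupported lambda-z and AUC0-tau values. Safety conclusions and escalation decisions do not depend on them. It is worth correcting because the correction needs no extra blood draws.

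**What to change.** In Table 9 and the matching PK text:

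1. Delete lambda-z and replace AUC0-tau with AUC0-4h.
2. Label Cmax and tmax as observed over 0-4 h, and flag patients whose highest value is the 4 h sample.
3. Report the predose and Day 140 (Day 112 at 32 mg) concentrations with actual sampling times. The schedule notes let predose PK blood be drawn up to a week before dosing, and the late visit has its own window.
4. Compare first-dose and last-dose exposure only on the shared predose, 1, 2 and 4 h times.
5. State that full-interval exposure and a terminal rate are not estimable by noncompartmental analysis from this grid. If either is wanted, it needs later samples or a prespecified population PK model.

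A first-dose terminal rate is optional and not part of this fix. At 2-16 mg, single-dose patients have Day 14, Day 28 and a Day 56 predose sample before any second dose, but Table 8 never promised that parameter.

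The cost is a text edit. The downside is that total exposure over the multiple-dose interval is no longer claimed, and AUC0-4h describes only a small part of it (about 2-35% in the assumed models).

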## 10.5 PHARMACODYNAMIC ANALYSES

Pharmacodynamic analyses will be performed for all patients in the PD population. Summary statistics will be provided for PD endpoints by dose cohort and visit. The change from baseline (Day 1) to the last measured time point will be determined. Individual patient data will be listed. Additional details on the statistical analysis of PD endpoints will be provided in the SAP.

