#### **Pharmacodynamics**

- Concentration of mHTT protein in CSF predose (baseline value) and at the last measured time point.

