#### **Clinical Effects**

- Change from baseline (baseline value to the last measured time point) and difference from placebo in the TFC, administered as part of the UHDRS.

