## **Exploratory Endpoints**

- Change from baseline (baseline value to the last measured time point) and difference from placebo in the motor, cognitive, independence, and functional assessments administered as part of the UHDRS.
- Change from baseline (baseline value to the last measured time point) and difference from placebo in the PBA-s.
- Changes from baseline MRI of the brain (Screening to last measured time point ).

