### 10.8.1 Unified Huntington's Disease Rating Scale

Summary statistics will be provided for each subtest of the UHDRS (TFC, motor, cognitive, independence, and functional assessments) by dose cohort and visit. A composite score of some or all of the components of the UHDRS may also be calculated. The change from baseline to the last measured time point will be determined. Individual patient data will be listed. Additional details on the statistical analysis of UHDRS data will be provided in the SAP.

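### TFC, the other UHDRS scores and PBA-s are defined against placebo, but the analysis section specifies no placebo contrast; one baseline-adjusted model with pooled placebo would supply it from data already collected

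*Combined protocol and SAP*

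**What the plan says.** Section 3.2 gives the secondary clinical endpoint as "Change from baseline (baseline value to the last measured time point) and difference from placebo in the TFC, administered as part of the UHDRS". The exploratory endpoints follow the same pattern, for example "Change from baseline (baseline value to the last measured time point) and difference from placebo in the PBA-s", and the remaining UHDRS subtests are worded likewise.

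The analysis text is thinner. Section 10.8.1 provides summary statistics for each subtest and adds: "The change from baseline to the last measured time point will be determined". Section 10.8.2 does the same for PBA-s. Neither names a comparison with placebo. Both defer further detail; for the UHDRS the sentence is "Additional details on the statistical analysis of UHDRS data will be provided in the SAP".

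For mHTT, Section 3.2 defines the endpoint as "Concentration of mHTT protein in CSF predose (baseline value) and at the last measured time point", with no mention of placebo. Section 3.1 nevertheless makes the PD effect on mHTT a secondary objective. Section 10.5 says "Summary statistics will be provided for PD endpoints by dose cohort and visit" and then "Additional details on the statistical analysis of PD endpoints will be provided in the SAP".

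Sections 4.1.3 and 6.1 make a dose cohort 12 patients, 9 on active drug and 3 on placebo. Section 10.9 summarises safety by treatment group as well as by dose cohort; Sections 10.5 and 10.8 mention only the dose cohort. Section 10.1 describes the analyses as mainly descriptive, with confidence intervals where suitable.

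**The concern.** An endpoint defined as a difference needs an estimator of that difference: which patients form the comparator, at which visit, with which covariates and with what interval. Section 10 gives none of these for the endpoints that Section 3.2 defines against placebo. Read literally, summaries by dose cohort would even merge active and placebo patients.

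If the tables are built from this text alone, readers will take differences by eye between groups of 9 and 3, without an interval and without allowance for where the groups started. Section 10.10 also permits unblinded summaries by treatment group, including mHTT, during the study. A comparator, visit or model chosen after such a look would be open to the charge that it was chosen on the data.

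**Working it through.** **1. Endpoint text against analysis text**

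| Measure | Endpoint (3.2) | Analysis (10.5, 10.8) | Gap |
|---|---|---|---|
| TFC (secondary) | change and placebo difference | summaries; change | no contrast |
| Other UHDRS scores (exploratory) | change and placebo difference | summaries; change | no contrast |
| PBA-s (exploratory) | change and placebo difference | summaries; change | no contrast |
| mHTT (secondary) | level at baseline and last time point | summaries; change | no endpoint mismatch; the objective lacks a comparison |

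No covariate or placebo pooling rule appears anywhere in Section 10.

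**2. The plan's own precision figure.** Section 10.2 gives a 90% interval of about ±110 fM for mHTT with n = 9. This is a one-group statement. The SD is not in the documents, so the figure can only be solved backwards: SD = 110 × √9 / t(0.95, 8 df) = 330 / 1.8595 = 177.5 fM (or 330 / 1.645 = 201 fM with a normal quantile). I use 177.5 fM as an assumption. It sets the widths below but cancels from the ratios.

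**3. Contrast in one model: five doses and pooled placebo.** Inputs: 9 per dose, 5 × 3 = 15 placebo, N = 60, six groups. The correlation rho between baseline and follow-up is not in the documents, so a range is shown. Equal SD at both times is assumed.

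- Multiplier: √(1/9 + 1/15) = 0.422.
- Change score: half-width = t(54 df) × SD × √(2(1 − rho)) × 0.422.
- Baseline-adjusted: half-width = t(53 df) × SD × √((1 − rho²)(1 + 1/52)) × 0.422. The factor 1 + 1/52 is the expected price of estimating the covariate slope.

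At rho = 0.7, t is 1.674 for both, and 1.674 × 177.5 × 0.422 = 125 fM. Change score: 125 × √0.6 = 97 fM. Adjusted: 125 × √(0.51 × 1.019) = 90 fM. The ratio is 0.93.

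| rho | Change (fM) | Adjusted (fM) | Ratio | CI narrower by |
|---|---|---|---|---|
| 0.5 | 125 | 109 | 0.88 | 12% |
| 0.7 | 97 | 90 | 0.93 | 7% |
| 0.8 | 79 | 76 | 0.96 | 4% |
| 0.9 | 56 | 55 | 0.98 | 2% |

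**4. The same comparison inside one cohort, 9 v 3.** With 10 and 9 residual df and a slope price of 1 + 1/8, the ratios at rho 0.5, 0.7, 0.8 and 0.9 are 0.93, 0.99, 1.02 and 1.05. Simulation at 0.5, 0.8 and 0.9 gave 0.92, 1.01 and 1.04. Adjustment stops helping at rho of about 0.75.

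**5. Chance baseline imbalance against pooled placebo.** One SE of the baseline difference for 9 v 15 is 0.42 SD. It moves a change-score difference by (1 − 0.7) × 0.42 = 0.13 SD at rho 0.7. The SE of that difference is √0.6 × 0.422 = 0.327 SD, and 0.126² / 0.327² = 0.15. That is exactly the large-sample variance saving, 1 − (1 + 0.7)/2 = 0.15. So the imbalance is the source of the gain in step 3, not a further gain.

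**6. Aligning the schedules.** Tables 1 and 2 end UHDRS and PBA-s at Day 140 (last dose Day 112) and, for 32 mg, Day 112 (last dose Day 84): both 28 days after the last dose. Final CSF is at Day 196 and Day 168: both 84 days after it. A visit counted from the last dose therefore exists for every cohort.

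**The case against.** The strongest reply is that the detail is deferred. Sections 10.1, 10.5, 10.8.1 and 10.8.2 all point to a SAP, and the supplied text contains none of it. A reader might infer that no placebo comparison is planned or that the endpoint will go unestimated; the documents do not support that. What can be said is that the contrast is not specified here.

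A reader might also infer that the protocol commits to an inferior raw change-score contrast. It does not. Saying that the change will be determined derives a variable; it does not prescribe an unadjusted comparison. Modelling the change with baseline as covariate gives the same treatment estimate as modelling the follow-up value, so the wording is compatible with the fix.

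Two statistical overreadings should also be set aside. Under randomisation the change-score contrast is unbiased, and chance imbalance is already in its standard error. Nor is adjustment more precise in every setting: inside a 9 v 3 cohort it is neutral or slightly worse at high correlation.

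Finally, the study is descriptive, its primary objective is safety, and its sample size does not rest on a test. That limits the weight of this point. It does not remove the need to say how a named secondary endpoint will be computed, and an estimate with an interval fits a descriptive plan.

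**Conclusion.** The point holds as a gap in specification. TFC, the other UHDRS scores and PBA-s are defined against placebo, and the analysis sections give no contrast, covariate or pooling rule. For mHTT only the objective lacks a comparison; the endpoint itself is consistent with Section 10.5.

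The benefit of baseline adjustment is real but modest: about 12% to 2% narrower intervals over rho 0.5 to 0.9, and only in one model with pooled placebo. These ratios assume normal data, equal SD at both times, complete data on 60 patients and exchangeable placebo patients. The fM widths also rest on a back-solved SD. Specifying the contrast in advance matters more than the precision gained.

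**What to change.** Before any unblinded summary under Section 10.10, state in the SAP for TFC, the other UHDRS scores, PBA-s and mHTT:

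- One linear model per endpoint across all cohorts, with treatment (each dose, pooled placebo) and the patient's own pre-first-dose value as covariate. This also settles the baseline for patients entering directly into multiple dosing: Section 10.5 says Day 1, while Table 3 uses Day 56 (Day 28 for 32 mg).
- A named analysis visit counted from the last dose, so that the 32 mg schedule lines up with the others.
- Each dose minus pooled placebo with a 90% CI and no formal test, beside descriptive tables split by treatment and dose.
- A sensitivity analysis using own-cohort placebo, or leaving the 32 mg cohort out of the pooling.
- That placebo patients belong to the analysis sets: Section 10.3.1 defines the Safety population by receipt of the active drug and builds the PD and Per Protocol populations on it.

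A log scale for mHTT is optional. The cost is SAP wording, one model per endpoint and one degree of freedom. The model also assumes linearity, which needs checking for bounded scores (TFC entry is limited to 7 to 13; PBA-s items are severity-by-frequency products), and that placebo patients can be pooled across cohorts.

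No new data are needed.

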## 10.6 IMMUNOGENICITY ASSESSMENT

Immunogenicity analyses will be performed for all patients. Summary statistics will be provided as appropriate. Individual patient data will be listed. Additional details on the statistical analysis of immunogenicity will be provided in the SAP.

## 10.7 MAGNETIC RESONANCE IMAGING

Summary statistics will be provided for MRI data by dose cohort and visit. Individual patient data will be listed. Additional details on the statistical analysis of MRI data will be provided in the SAP.

## 10.8 CLINICAL EFFECTS ANALYSES

Clinical effects analyses will be performed for all patients in the Per Protocol population.

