## **9 ADVERSE EVENTS**

The Investigator is responsible for reporting all AEs that are observed or reported during the study, regardless of their relationship to study treatment or their clinical significance.

Adverse events will be assessed beginning at enrollment (date of signed informed consent) and up to the end of the study.

An AE is defined as any untoward medical occurrence in a patient enrolled into this study regardless of its causal relationship to study treatment. Patients will be instructed to contact the Investigator at any time after randomization if any symptoms develop.

A TEAE is defined as any event not present before exposure to study treatment or any event already present that worsens in either intensity or frequency after exposure to study treatment (excluding worsening of results on the UHDRS or PBA-s rating scales).

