### **9.1 ELICITING AND DOCUMENTING ADVERSE EVENTS**

All AEs reported or observed during the study, including AEs resulting from concurrent illnesses, reactions to concurrent medications, or progression of disease states, will be recorded on the AE page in the eCRF and in the site source notes. The eCRFs used to document AEs are designed to help ensure this information is collected in a standard manner. Information to be collected includes event term, date and time of onset, date and time of resolution, Investigator-specified assessment of severity and relationship to study treatment, action taken with respect to study treatment, seriousness, any required treatment or evaluations, and outcome. All AEs will be followed to adequate resolution. The sites will be provided completion guidelines for the eCRF, which will further guide them on how to record the data, including AEs. The MedDRA will be used to code all AEs.

Any medical condition that is present at the time that the patient is screened but does not worsen should not be reported as an AE. However, if it worsens at any time during the study, this should be recorded as an AE. This includes any spontaneously reported worsening of depression (ie, not based on the study rating scales).

In addition to observations of the patient, AEs identified from any study data (eg, laboratory values, physical examination findings, ECG changes, C-SSRS) or identified from review of other documents that are considered clinically significant will be documented on the AE page in the eCRF. The eCRFs also include a form specifically for a detailed neurological assessment, with instructions to report any worsening as an AE. Worsening of symptoms that are only detected on clinical effects rating scales will not be reported as AEs.

Adverse events (AEs) will be solicited at each visit by direct questioning as well as elicited from physical and neurological examination by site staff. In addition, all sites in the study must ensure patients have a 24-hour telephone number to contact medical site staff for the duration of the study, in case of emergent AEs or SAEs.

If there is any doubt as to whether a clinical observation is an AE, the event should be reported. Adverse events characterized as intermittent do not require documentation of onset and duration of each episode.

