## 10.3 STUDY PATIENTS

### 10.3.1 Analysis Populations

The following study populations will be evaluated:

- Safety population will include all randomly assigned patients who receive at least 1 dose of WVE-120101.
- PD population will include all patients in the safety population who have at least 1 postbaseline CSF sample.
- PK population will include all patients in the safety population who have sufficient plasma or CSF concentration data, as determined by the pharmacokineticist, for inclusion in the descriptive statistical analysis.
- Per Protocol Population will include all patients in the Safety population who have no major protocol deviations.

The Safety population will be used for the safety analysis, demographics, and other baseline patient characteristics; the PD population will be used for the PD analysis; the PK population will be used for the PK analysis; and the Per Protocol population will be used for all analyses of clinical effects.

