### 10.3.4 Protocol Deviations

Assessment of protocol deviations as ‘minor’ or ‘major’ will be determined blinded to treatment and prior to database unblinding. A protocol deviations log will be finalized before unblinding and final database lock. Protocol deviations will be presented by patient in a data listing.

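### All summaries of clinical effects, including the secondary TFC endpoint, use only the Per Protocol population, and no analysis of all treated patients is named

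*Combined protocol and SAP*

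**What the plan says.** Two places in the protocol fix the population. Section 10.8: "Clinical effects analyses will be performed for all patients in the Per Protocol population". Section 10.3.1: "the Per Protocol population will be used for all analyses of clinical effects". Section 10.3.1 also defines the set, "Per Protocol Population will include all patients in the Safety population who have no major protocol deviations", and its parent, "Safety population will include all randomly assigned patients who receive at least 1 dose of WVE-120101".

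Under Section 10.3.4, the classification of deviations as minor or major "will be determined blinded to treatment and prior to database unblinding". Neither that section nor Section 14.2.2 gives criteria for a major deviation.

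The secondary clinical endpoint in Section 3.2 is: "Change from baseline (baseline value to the last measured time point) and difference from placebo in the TFC, administered as part of the UHDRS".

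On adverse events, Section 9 defines a TEAE "excluding worsening of results on the UHDRS or PBA-s rating scales", and Section 9.1 adds: "Worsening of symptoms that are only detected on clinical effects rating scales will not be reported as AEs". Section 9.1 also provides a detailed neurological assessment form, on which any worsening is to be reported as an AE.

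Sections 10.1, 10.8.1 and 10.8.2 call for listings of individual patient data and do not say which population the listings cover. Sections 10.8.1 and 10.8.2 leave further analysis detail to a separate SAP, whose text is not in the document at hand.

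**The concern.** A Per Protocol set is defined by what happens in the trial. If a departure from the protocol is linked to how well a patient tolerates repeated intrathecal dosing, or to decline in Huntington's disease, then dropping that patient changes who is compared with whom. Using such a set as a sensitivity analysis is ordinary practice. Here it is the only set named for the scales.

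The adverse-event rules add to this. Worsening that shows only on the UHDRS or PBA-s is kept out of the AE tables by design, so the clinical-effects tables are the summaries in which it would be seen. A patient excluded from Per Protocol disappears from those too. In a trial whose primary objective is safety and tolerability, group-level evidence of functional or behavioural decline should not depend on an undefined exclusion rule.

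**Working it through.** **1. Is the restriction stated, and is it complete?** Sections 10.3.1 and 10.8 agree, and neither qualifies the other. No other population is attached to the UHDRS or PBA-s summaries anywhere in the protocol.

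**2. Would the excluded data exist?** Usually. Section 5.3.2 encourages patients who stop treatment to stay for safety follow-up and asks for an early termination visit whenever possible. Tables 1, 2 and 3 schedule the UHDRS and PBA-s at that visit. For a patient with a major deviation the values would be collected and then left out of the summaries.

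**3. Where would scale-only worsening appear?**

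| Output | Patient in Per Protocol | Patient outside Per Protocol |
|---|---|---|
| AE summary tables (Sections 9, 9.1, 10.9.1) | no | no |
| Clinical-effects summary tables (Section 10.8) | yes | no |
| Individual listings (Sections 10.1, 10.8.1, 10.8.2) | yes | population not stated |

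Worsening that is also found on the neurological form is reported as an AE in either case.

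**4. How far can exclusion move a mean?** Section 6.1 gives 9 active and 3 placebo patients per cohort; five cohorts give 5 × 12 = 60, which reproduces the planned enrolment. Let k of n patients be excluded, with mean change mR in those retained and mE in those excluded. The mean of all n is [(n − k)mR + k·mE]/n, so

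mR − mean of all = (k/n)(mR − mE).

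For n = 9 the multiplier is 1/9 = 0.11, 2/9 = 0.22 or 3/9 = 0.33 for k = 1, 2 or 3.

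**5. What happens to precision?** Assume an unchanged SD and a t-based 90% interval (the level used in Section 10.2 for mHTT; none is given for the scales). The half-width in SD units is t/√n: 0.620 for 9 patients, 0.670 for 8, 0.734 for 7 and 0.823 for 6. The interval is wider by about 8%, 18% and 33% after losing 1, 2 and 3 patients.

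**6. How often would this arise?** The documents give no major-deviation rate. At assumed rates of 5%, 10% and 20%, with independent patients, the chance that an active group of 9 loses at least one is 1 − 0.95⁹ = 37%, 1 − 0.90⁹ = 61% and 1 − 0.80⁹ = 87%. The expected loss among 60 is 3, 6 and 12.

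**7. Is the direction known?** Two illustrations with assumed values point opposite ways. If 2 of 9 active patients fall 1 TFC point and are excluded while 7 are stable, the active mean goes from 2 × (−1)/9 = −0.22 to 0, which favours the drug. If 1 of 3 placebo patients falls 1 point and is excluded while 2 are stable, the placebo mean goes from −0.33 to 0, which counts against the drug. With placebo pooled over cohorts (15 patients) the latter shift would be 1/15 = 0.07; the protocol does not say whether placebo is pooled.

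**8. Is there a comparator in the set?** Per Protocol is a subset of Safety, and Safety as worded requires a dose of WVE-120101. A placebo patient receives none, so read literally neither set contains placebo patients, and the difference from placebo in Section 3.2 cannot be formed. The primary endpoint in Section 3.2, also compared with placebo, and the reporting by treatment group in Section 10.9 indicate that this was not intended.

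The plan's one precision figure, about ±110 fM for mHTT in Section 10.2, concerns another endpoint. It cannot be reproduced without an SD and does not bear on this point.

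**The case against.** The strongest reply is that the exclusions may have little to do with tolerability. Section 14.2.2 describes a deviation as unintended or unanticipated. Stopping under Section 4.3.4.2 and withdrawal under Sections 5.3.1 and 5.3.2 are provided for in the protocol, so they need not count as deviations. Major deviations might largely be eligibility breaches that precede randomisation. Classification is blinded and completed before unblinding. The analyses are mainly descriptive, the sample size rests on no hypothesis test, TFC is one secondary endpoint, and the SAP may add detail. Nor is the comparison purely randomised under any set, because direct entrants to multiple dosing receive a matched assignment (Section 6.1).

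Much of this stands. A reader might infer that patients who stop for toxicity are dropped, or that missed doses are major deviations; the documents say neither. A reader might also infer that the bias favours the drug; step 7 shows that this depends on who is excluded. And a reader might conclude that scale-only worsening vanishes altogether for excluded patients. The documents do not support that, since individual data are to be listed and the neurological form is a separate route to AE reporting.

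What does not answer the point: blinding prevents knowing selection but does not break a link between deviation and outcome; a listing gives no group comparison; and a deferral of details does not displace a population that the protocol has already fixed.

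**Conclusion.** The concern holds in a limited form. The only planned summaries of the clinical scales, and the only planned comparison with placebo on them, use a set with an undefined exclusion rule, although post-baseline values would usually be available for the patients left out. For those patients, scale-only worsening is absent from every summary table. Each excluded active patient moves a cohort mean by one ninth of the retained-minus-excluded difference. How many patients are affected, and in which direction, cannot be established from the documents; the rates and TFC values in steps 6 and 7 are assumptions. The literal Safety wording is a further defect, since it leaves the set without placebo patients.

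This should be fixed but is not critical. The harm is to estimates and to the functional and behavioural side of the tolerability picture. There is no error rate to inflate, and AE analyses have their own population.

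**What to change.** In Sections 10.3.1 and 10.8, and in the SAP:

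- Make the main clinical-effects set all randomised or assigned patients who received any study treatment, active or placebo, and have a baseline and at least one post-baseline value, analysed by assigned treatment.
- Keep Per Protocol as a sensitivity analysis, and state the criteria for a major deviation.
- Carry the active-or-placebo wording into the Safety definition, since otherwise the Per Protocol sensitivity analysis keeps the same gap.
- State that the UHDRS and PBA-s listings cover all treated patients.

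These changes should be settled before any unblinded summaries, including the administrative analyses allowed by Section 10.10. The cost is revised wording and one more set of tables; no new data are needed. The new set still omits patients with no post-baseline value, and it does not make the comparison purely randomised where direct entrants are included.
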